2. RESEARCH PLAN

Purpose of Study:
To compare scar infiltration with 0.5-1% Lidocaine at a dose of 3 mg/kg (max dose 300 mg) or scar deactivation with acupuncture surface release technique to determine which is more effective in reducing pain in adult patients with chronic, post-surgical pain related to the site of incision after low transverse Cesarean section compared to standard of care physical therapy with the McKenzie Method.
Hypotheses, Research Questions, or Objectives:

 • Objective 1: Compare whether a scar infiltration protocol with Lidocaine is more effective than scar deactivation with acupuncture surface release technique at improving pain in adults with chronic, post-surgical pain related to low transverse Cesarean section incision. • Null Hypothesis 1: 0.5-1% Lidocaine at a dose of 3 mg/kg (max dose 300 mg) does not reduce pain outcomes acutely and over time. • Null Hypothesis 2: Scar deactivation with acupuncture surface release technique does not reduce pain outcomes acutely and over time. • Alternative Hypothesis 1: 0.5-1% Lidocaine at a dose of 3 mg/kg (max dose 300 mg) reduces pain outcomes acutely and over time. • Alternative Hypothesis 2: Scar deactivation with acupuncture surface release technique reduces pain outcomes acutely and over time.
Significance:
According to CDC 2015 data, 32% of all births are delivered via Cesarean section ¹ . In patients who undergo Cesarean section, studies estimate 7-18% will experience chronic post-operative pain at the site of their incisional scar ² . These statistics indicate that up to 1 in 6 out of every pregnancy is at risk of developing postoperative pain with an increased risk with each subsequent Cesarean section, and a significant portion of these members will seek care in the primary care clinic.
Military Relevance:

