In 2016, the Department of Defense employed 1,288,596 active duty service members, of which 15.9% were women ³ . This age range is consistent with peak childbearing age, which extrapolates to a large portion of the female active duty force with the potential to have children during their military careers. Determining whether Scar infiltration or scar deactivation is more effective treatments for the reduction of chronic, post-surgical low transverse Cesarean section pain in military beneficiaries would result in less: lost duty days, profiles, and physical fitness testing exemptions in our active duty population, as well as an improved quality of life for all DoD beneficiaries. Scar infiltration is a technique using high dose and high volume lidocaine to infiltrate the scar. Scar infiltration uses 40cc to 60cc of 0.5% to 1% lidocaine, which is injected throughout the scar with a goal of 3-4mg/kg per injection. Typically a series of 4 to 5 injections. Scar deactivation is a technique when acupuncture needles are inserted into the skin surrounding the scar and are left in place for approximately 20 minutes and then removed. This can be repeated multiple times.

Background and Review of Literature:

Existing Knowledge: The etiology of chronic, post-surgical abdominal wall and/or pelvic pain after Cesarean section has multiple hypotheses. These possible sources include development of intra-peritoneal adhesions restricting fascial planes, anterior cutaneous nerve entrapment, and disruption of the autonomic nervous system within the intracellular fluid matrix known as an “interference field”^{2,4,5,6,7}. While there is not a clearly established and widely accepted pathophysiological cause to this post-operative pain, studies have estimated that between 7-33% of patients experience chronic peri-incisional pain after Cesarean section with Pfannenstiel incision – a type of abdominal surgical incision that allows access to the abdomen and the most common method for performing Cesarean sections today – defined as pain persisting beyond the period of expected healing, approximately 3 months^{2,7}.

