 - Alternating placement of Spring Ten (0.30x40 mm) acupuncture needles to surround scar left in place for a treatment duration of 20 minutes. Needles will be placed at intervals of 1cm to 1.5 cm and will surround the scar with a maximum of 20 needles per treatment.
 - **Group 2: Scar Infiltration with 0.25-1% Lidocaine:**
 - Will consist of calculation of 3 mg/kg dose of 0.5-1% Lidocaine and a dermal followed by subcutaneous injection using 1.5 inch 25 G needle and syringe appropriate for volume based on calculated dose.
 - **Group 3: Physical therapy:**
 - Will be a referral to physical therapy specifying McKenzie protocol treatment for the presenting complaint. The McKenzie protocol is a form of standard of care physical therapy in which the physical therapist tries to find a cause and effect relationship between the positions the patient usually assumes while sitting, standing, or moving, and the location of pain because of those positions or activities. The therapeutic approach requires a patient to move through a series of activities and test movement to gauge the patient's pain response. The approach then uses that information to develop an exercise program designed to centralize or alleviate the pain.

Visit 1 (may be same day as screening visit) (visit window plus or minus 1 week):

Group 1: Scar Deactivation Surface Release Technique protocol (acupuncture):

- Study staff will reconcile medication list (including analgesic medication currently taking).
- Subjects will be weighed (in pounds-not stated weight).
- We will ask what the subjects' expectations are regarding acupunctures effectiveness for chronic, post-surgical pain related to low transverse Cesarean Section.
- The Research Coordinator will record the number of needles placed and the name of the provider performing the acupuncture.
- **Pre-Treatment:**
 - Defense and Veterans Pain Rating Scale (DVPRS)
 - Instruct patients to mark general area of scar on pictures provided on the Patient and Observer Scar Assessment Score (POSAS) Patient Scale.
 - Instruct the PI or AI to complete the POSAS Observer Scale.
- **Post-Treatment:**
 - DVPRS
 - Instruct patients to mark general area of scar on pictures provided the POSAS Patient Scale.
 - Instruct the PI or AI to complete the POSAS Observer Scale.

Group 2: Scar Infiltration with 0.25-1% Lidocaine:

- Study staff will reconcile medication list (including analgesic medication currently taking).

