- Subjects will be weighed (in pounds-not stated weight).
- We will ask what the subjects' expectations are regarding lidocaine's effectiveness for chronic, post-surgical pain related to low transverse Cesarean Section.
- The Research Coordinator will document the total volume of 0.5-1% Lidocaine injection.
- **Pre-Treatment:**
 - DVPRS

- Instruct patients to mark general area of scar on pictures provided on the POSAS Patient Scale.
- Instruct the PI or AI to complete the POSAS Observer Scale.
- Post-Treatment:
 - DVPRS
 - Instruct patients to mark general area of scar on pictures provided the POSAS Patient Scale.
 - Instruct the PI or AI to complete the POSAS Observer Scale.

Group 3: Physical Therapy:

- Study staff will reconcile medication list (including analgesic medication currently taking).
- Subjects will be weighed (in pounds-not stated weight).
- We will ask what the subjects' expectations are regarding physical therapy's effectiveness for chronic, post-surgical pain related to low transverse Cesarean Section.
- Subjects will be given a study diary and asked to track the dates and duration of their physical therapy treatments.
- DVPRS
- Instruct patients to mark general area of scar on pictures provided on the POSAS Patient Scale.
- Instruct the PI or AI to complete the POSAS Observer Scale.

Visit 2 (4 weeks after visit 1 (visit window plus or minus 1 week)):

Group 1: Scar Deactivation Surface Release Technique protocol (acupuncture):

- Study staff will reconcile medication list (including analgesic medication currently taking).
- Subjects will be weighed (in pounds-not stated weight).
- The Research Coordinator will record the number of needles placed and the name of the provider performing the acupuncture.
- Pre-Treatment:
 - DVPRS
 - Instruct patients to mark general area of scar on pictures provided on the POSAS Patient Scale.
 - Instruct the PI or AI to complete the POSAS Observer Scale.
- Post-Treatment:
 - DVPRS
 - Instruct patients to mark general area of scar on pictures provided the POSAS Patient Scale.
 - Instruct the PI or AI to complete the POSAS Observer Scale.

Group 2: Scar Infiltration with 0.25-1% Lidocaine:

- Study staff will reconcile medication list (including analgesic medication currently taking).
- Subjects will be weighed (in pounds-not stated weight).
- The Research Coordinator will document the total volume of 0.5-1% Lidocaine injection.
- Pre-Treatment:
 - DVPRS

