- Study staff will reconcile medication list (including analgesic medication currently taking).
- Subjects will be weighed (in pounds-not stated weight).
- DVPRS
- Instruct patients to mark general area of scar on pictures provided on the POSAS Patient Scale.
- Instruct the PI or AI to complete the POSAS Observer Scale.
- We will record the subjects self-reported reduction in pain severity since the beginning of the study (reported a percentile (i.e. 10%, 20%, etc.).
- We will ask if the subjects' expectations were met regarding acupunctures effectiveness for chronic, post-surgical pain related to low transverse Cesarean Section.

Group 2: Scar Infiltration with 0.25-1% Lidocaine:

[figure not shown]
- Study staff will reconcile medication list (including analgesic medication currently taking).
- Subjects will be weighed (in pounds-not stated weight).
- DVPRS
- Instruct patients to mark general area of scar on pictures provided on the POSAS Patient Scale.
- Instruct the PI or AI to complete the POSAS Observer Scale.
- We will record the subjects self-reported reduction in pain severity since the beginning of the study (reported a percentile (i.e. 10%, 20%, etc.).
- We will ask if the subjects' expectations were met regarding lidocaine's effectiveness for chronic, post-surgical pain related to low transverse Cesarean Section.

Group 3: Physical Therapy:

- Study staff will reconcile medication list (including analgesic medication currently taking).
- Subjects will be weighed (in pounds-not stated weight).
- DVPRS
- Instruct patients to mark general area of scar on pictures provided on the POSAS Patient Scale.

- Instruct the PI or AI to complete the POSAS Observer Scale.
- We will record the subjects self-reported reduction in pain severity since the beginning of the study (reported a percentile (i.e. 10%, 20%, etc.).
- We will ask if the subjects' expectations were met regarding physical therapies effectiveness for chronic, post-surgical pain related to low transverse Cesarean Section.

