----------------------------	--	------------------------------	--

Participation Compensation: Subjects will not be paid for participation in this study.

Assent Process: N/A

Benefits:

Subjects may experience an improvement in pain in both the treatment groups; however, this is not a guarantee.

Risks:

The potential risks to participate in this study are minimal. The risks associated with participating in this research study include:

Acupuncture Risks:

- Likely and not serious:
 - Pain
 - Bleeding
- Less Likely and not serious:
 - Infection
 - Muscle cramps/spasms
- Less Likely and serious:
 - Bowel Perforation
 - Transient vasovagal response to needling

Lidocaine Risks:

- Likely and not serious:
 - Pain
 - Bleeding

- Less Likely and not serious:
 - Infection
 - Lidocaine toxicity

These risks will be minimized by cleaning the treatment site with an alcohol swab prior to placement. If at any time the patient reports a side effect, they will be referred to one of the Investigators for care. There may be a risk of inadvertent breach of confidentiality.

Costs: N/A

Safeguards for Protecting Information:

The research consents and HIPAA Authorization Documents will be stored in a locked cabinet in a locked room with restricted access. All identifiable research data including patient demographics will be kept in an electronic database separate from the coded research data, which will be encrypted, double password protected and the access will be restricted. The research data will be coded and any links to identifiable data (i.e., Master Key) will be destroyed as soon as all data mergers have occurred, or no later than at the closure of the study, all identifiable patient information will be destroyed based on AFI 33-332, "The Air Force Privacy and Civil Liberties Program" and the National Institute of Standards and Technology Special Publication (NIST SP 800-88) for the approved methods to destroy PII. The anonymized research data will not be utilized for further research activity beyond the protocol stipulations without additional IRB approval. At the conclusion of the study, the data will be de-identified prior to review and analysis.

Data and Specimen Storage Plan

How will coded or identifiable data/specimens be stored?

	Paper data, including completed consent forms	The research consents and HIPAA Authorization Documents will be stored in a locked cabinet in a locked room with restricted access.

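### The lidocaine arm's procedure omits the 300 mg maximum set in the Research Plan; secondarily, no visit list asks about adverse effects

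*Combined protocol and SAP*

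**What the plan says.** **Dose.** Section 2 (Research Plan) defines the lidocaine treatment as "0.5-1% Lidocaine at a dose of 3 mg/kg (max dose 300 mg". The maximum appears three times there: in the Purpose and in the null and alternative hypotheses for lidocaine. The Military Relevance text in the same section describes the technique in general, "with a goal of 3-4mg/kg per injection", with no maximum. In section 3, under Randomization, the Group 2 procedure reads "Will consist of calculation of 3 mg/kg dose of 0.5-1% Lidocaine and a dermal followed by subcutaneous injection" and sizes the syringe to the volume that results. It states no maximum. At Visits 1 to 4 the Group 2 lists record the volume injected.

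**Prevention.** The Risks part of section 4 lists lidocaine toxicity among the less likely, non-serious risks. The one preventive measure that follows is: "These risks will be minimized by cleaning the treatment site with an alcohol swab prior to placement".

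**Adverse effects.** The same part says: "If at any time the patient reports a side effect, they will be referred to one of the Investigators for care". The sentence recurs under the safeguards for subjects, and the Clinical Care paragraph promises treatment or referral for an injury or adverse effect. Data Safety Monitoring is marked not applicable. The Visit 1 to 5 lists cover medication reconciliation, weight, the DVPRS, both POSAS scales, expectations, needle count or lidocaine volume, the physical therapy diary and, at Visit 5, a self-rated percentage reduction in pain. None includes a question about side effects.

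**The concern.** A dose limit protects subjects only if it stands in the text that staff follow when they draw up the drug. Here it stands in the statement of purpose and the hypotheses, while the procedure lets the dose rise with weight without end. The Risks section does not repair this, because cleaning the skin bears on infection and not on systemic toxicity.

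The second matter is ascertainment. Referral and care are responses to a report; neither schedules a question. An effect that the subject does not mention, and that no pain or scar score shows, may be unknown when the next needle treatment is given 4 or 8 weeks later. In the final report, a count of zero could then mean that nothing happened or that nothing was volunteered. This applies to both needle arms. The only risks labelled serious, "Bowel Perforation" and a vasovagal response, are listed for acupuncture.

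**Working it through.** **Dose.** The inputs are 3 mg/kg and 300 mg (section 2), and 3 mg/kg with no maximum (section 3, Group 2). The eligibility criteria list no weight limit.

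- Weight at which the two texts part: 300 / 3 = 100 kg, or 100 × 2.20462 = 220.5 lb. Subjects are weighed in pounds.
- Excess above that weight: 3 × (kg − 100) mg.

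The protocol gives no weight distribution, so the weights below are assumptions.

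| Weight (kg) | Group 2 procedure alone (mg) | With the maximum (mg) | Excess (mg) |
|---|---|---|---|
| 80 | 240 | 240 | 0 |
| 100 | 300 | 300 | 0 |
| 110 | 330 | 300 | 30 |
| 120 | 360 | 300 | 60 |
| 140 | 420 | 300 | 120 |

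The recorded volume does not by itself show whether the maximum was kept. With mg = mL × % × 10, 40 mL is 200 mg at 0.5% and 400 mg at 1%.

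**What the visits could reveal.** I set the risks listed in section 4 against the items in the visit lists.

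- Pain: the DVPRS asks about it before and after each needle treatment at Visits 1 to 4, and at Visit 5.
- Scar changes, itching and other local effects: the POSAS Patient Scale may show them, and so may the investigator's scoring ("Instruct the PI or AI to complete the POSAS Observer Scale"). In the needle arms each scale is completed 4 × 2 + 1 = 9 times.
- A complication that led to a new drug: medication reconciliation at every visit, in every arm, may show it.
- Muscle spasm, vasovagal response and lidocaine toxicity: no item addresses them. Staff may see an event during treatment, but no item records it. One that occurs after the subject leaves depends on her raising it.
- Related and unrelated symptoms: the secondary outcomes in sections 3 and 6 mention them, with a questionnaire, but as reduction or improvement. They appear in no visit list.

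**Scale.** Equal arms are assumed. With 48 planned completers there are 48 / 3 = 16 per arm. Three repeat treatments each (Visits 2 to 4) give 16 × 3 = 48 per needle arm, 96 in all. If all 60 enrolled complete, there are 60 / 3 = 20 per arm and 20 × 3 = 60 per needle arm, 120 in all. In the available text, none of these 96 to 120 treatments is preceded by a solicited adverse-effect question.

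**The case against.** The strongest reply is that the limit is already in the protocol. It is stated three times, section 10 commits to using lidocaine according to its labeling, and subjects are actually weighed at each visit. A reader might infer from the Group 2 text that the trial has no dose limit, or that it authorises doses above 300 mg. The documents do not support that: the two texts use the same 3 mg/kg, and the maximum belongs to the treatment as defined in section 2. Nor is 3-4 mg/kg a study dose; it describes the technique in general. What stands is narrower: the maximum was not carried into the operative procedure.

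A reader might also infer that harms go unobserved between treatments. That is too strong. Pain, listed as likely in both needle arms, is asked about repeatedly, and the scar scales and medication reconciliation can bring other effects to light. The gap is confined to effects that these items do not reach.

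A further objection is that a harm question could colour self-reported outcomes when subjects know their treatment. This has force. Placing the item after the first DVPRS alone would not be enough, because the POSAS Patient Scale follows it and section 6 names POSAS as primary in one place and secondary in another. Asking more often in the needle arms than in physical therapy would also prompt the arms unequally. The fix below answers both, except that in the needle arms the post-treatment DVPRS and POSAS Patient Scale at Visits 2 to 4 would still follow the question.

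Finally, the Procedure Instructions, Form O and the consent document are not available. Any of them may hold the maximum or the question, so the absence is shown only for the available text.

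**Conclusion.** Both parts hold, at low severity. The main one is the missing maximum: dosing from the Group 2 procedure alone exceeds the trial's own limit for any subject over 100 kg, by 3 mg for each kg above it. How many subjects that concerns cannot be said from the documents and may be zero. No toxicity rate is given and none is assumed.

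The secondary part is that no visit list in the available text solicits adverse effects, so some listed effects rest on spontaneous report. The counts of 96 to 120 repeat treatments assume equal arms.

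The primary pain outcome is unaffected and no safety endpoint is planned. It should not be inferred that the added question would let a trial of this size rule out uncommon harm. Pain and bleeding are listed as likely, so positive answers are to be expected; the gain is a known number of subjects asked.

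**What to change.** 1. Add the 300 mg maximum to the Group 2 procedure in section 3. In the Risks part of section 4, cite 3 mg/kg with a 300 mg maximum as the measure against toxicity, and limit the swab sentence to infection. The cost is text edits only.

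2. Add one fixed adverse-effect item at Visits 2 to 5, identical in all three arms, covering the interval since the last visit including the previous treatment. Use the listed risks plus an open category, which also serves physical therapy, for which no risks are listed. Ask it after that visit's pre-treatment (or only) DVPRS and POSAS Patient Scale and before any treatment. Tabulate it by arm. If immediate effects are also recorded in the needle arms, do so after the post-treatment DVPRS and POSAS.

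3. If an attachment already holds the maximum or the question, carry it into the Group 2 procedure and the visit lists.

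Cost of item 2: 4 visits × 3 arms = 12 visit lists to amend, changes to the data forms, and one table. At four answers per subject there are 48 × 4 = 192 to 60 × 4 = 240 answers. At an assumed 1 to 2 minutes each, that is about 3.2 hours (192 × 1 / 60) to 8 hours (240 × 2 / 60) of staff time. The optional post-treatment record would amend 8 more lists. No visit or procedure is added. The remaining downside is a small possibility that the question influences the later post-treatment DVPRS at Visits 2 to 4.

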5. ALTERNATIVES

Alternatives:

Acupuncture and lidocaine for scar infiltration are done in the Family Medicine Residency as part of standard of care. However, other medicinal therapies, such as Acetaminophen or Non-Steroidal Anti-inflammatory Drugs, Tricyclic Antidepressants, Gabapentin, Pregabalin, and Serotonin-Norepinephrine Reuptake Inhibitors can be used. If medicinal therapy fails to manage symptoms, consultation for pain management specialists and/or surgical evaluation is often considered. Subjects may choose to receive any of these types of treatment options without participating in this study.

6. DATA ANALYSIS

Data Analysis:

Outcome Measures:

The primary outcome measures are the Patient and Observer Scar Assessment Scale (POSAS), and the Defense and Veterans Pain Rating Scale (DVPRS).

The Patient and Observer Scar Assessment Scale consists of the total score of two numeric scales measured by the patient and a qualified observer. Each scale assesses the scar by six characteristics on 10-point scales with a 1 corresponding to normal skin and a 10 representing the worst imaginable condition for that characteristic. The Total Score of both scales is calculated by summing scores of the six items resulting in a range of 6 to 60. The POSAS is treated as an interval variable; therefore, parametric methods will be used for this outcome¹⁷.

The DVPRS consists of an 11-point numerical rating scale with 0 indicating no pain and 10 indicating severe pain. It has been confirmed for reliability and validity in measuring both acute and chronic pain, and is currently the standard for pain measurement throughout DoD and VHA health systems. The DVPRS has demonstrated linear scale qualities allowing parametric methods to be used.^{18, 19}.

Outcome Measures:

Primary outcome: Pain reduction and reduction of DVPRS score. The goal for pain reductions will be 50% as a primary outcome.

Secondary outcomes: Reduction of POSAS score, improvement in related and unrelated symptoms as identified by above mentioned questionnaire, and willingness to undergo further treatment.

Sample Size Estimation/Power Analysis:

The study is organized as a mixed effects, randomized complete block design with repeated measures. Subject is a random effect as subjects will have been randomly subjected to C-section from the population of patients obtaining similar care at these Air Force medical treatment facilities, randomly enrolled from this population of patients, and randomly assigned to 3 treatment groups at the time of study enrollment. Fixed effects are treatment group and time of repeated measure as these effects cannot be generalized to other treatments and times.

A priori power was assessed using G*Power Version 3.1.9.2.²⁰ Mean (SD) Total POSAS scores for non-hypertrophic scars resulting from vertical incisions have been found to be 21.1 (8.3) and 21.4 (7.4).^{21,22,23} Power for the Total POSAS score was assessed to detect a 1 SD difference. Mean (SD) DVPRS pain intensity for a broad sample consisting of inpatients and outpatients suffering from acute and chronic pain has been found to be 4.4 (2.4), and will serve as the effect size for this outcome.

A priori power analysis for a rANOVA for the POSAS indicates 24 subjects will have a power of 0.966 to detect the minimal clinically important difference at alpha = 0.05. A priori power analysis for a rANOVA for the DVPRS indicates 33 subjects will have a power of 0.962 to detect the minimal clinically important difference at alpha = 0.05. Post hoc tests within smaller subgroups may be required, such as differences due to time within a treatment group. Therefore, to achieve a power for post hoc tests of 0.95 at alpha = 0.05, a sample size of 45 subjects will be required.

Statistical Analysis:

Sample and treatment group means and standard deviations will be calculated for normally distributed interval variables and medians and interquartile ranges (IQR) for non-normally distributed interval variables. Frequency distributions will be produced for nominal and ordinal variables.

The statistical hypotheses of null effects for POSAS and DVPRS outcome measures will be tested by a mixed effects repeated measures analysis of covariance (rANCOVA). In the event the rANCOVA null hypothesis is rejected, contrasts will be used to investigate effects and differences within time intervals.

In the event multiple comparison tests are used to investigate effects, the Holm method will be used to correct the significance level of α to $p = .05$.²⁴

[name], Senior Research Biostatistician Subject Matter Expert for Clinical Research Management under contracts OMNI 0004 3-82 and OMNI 0005 3-126, is the statistical consultant supporting this study. Statistical analysis will be performed with R Version 3.5.1.²⁵

Number of Subjects:

	# Planned to Enroll	# Enrolled	# Planned to Complete Study	TOTAL
Number of Subjects at Scott AFB	30	N/A	24	
Number of Subjects at Nellis AFB	30	N/A	24	60

**If one site recruits more than the other, then they will be able to continue recruitment until the accrual ceiling has been reached.*

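### The plan does not commit to adjusting for the Visit 1 pre-treatment score: the effects it lists are group and time only, and its rANCOVA names no covariate

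*Combined protocol and SAP*

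**What the plan says.** All modelling statements are in Section 6, Data Analysis.

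- **Model effects**, under Sample Size Estimation/Power Analysis: "Subject is a random effect", and "Fixed effects are treatment group and time of repeated measure as these effects cannot be generalized to other treatments and times". No other list of effects appears.
- **Power basis**, same heading: an rANOVA for each scale, which has no covariate. The DVPRS input is a mean and SD that "has been found to be 4.4 (2.4), and will serve as the effect size for this outcome".
- **Test**, under Statistical Analysis: the null hypotheses for POSAS and DVPRS "will be tested by a mixed effects repeated measures analysis of covariance (rANCOVA"). No covariate is named. If the null is rejected, "contrasts will be used to investigate effects and differences within time intervals".
- **Primary outcome**, under Outcome Measures: "Primary outcome: Pain reduction and reduction of DVPRS score", and "The goal for pain reductions will be 50% as a primary outcome".

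The visit schedule in Section 3 supplies the baseline. At Visit 1, Group 1 completes the "Defense and Veterans Pain Rating Scale (DVPRS") before treatment, and Group 2 does the same. Group 3 has one DVPRS at Visit 1. POSAS follows the same pattern. By the visit text, Groups 1 and 2 have two DVPRS readings at each of Visits 1 to 4 and one at Visit 5 (4 × 2 + 1 = 9). Group 3 has one per visit (5).

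**The concern.** The three descriptions of the analysis do not agree. The list of effects has no covariate, the power basis has none, and the test is named for a covariate that is never identified. Contrasts within time intervals need a group-by-time term, and none is listed.

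This matters because the primary outcome is a reduction and each arm holds about 15 or 16 women (45/3 by the power statement, 48/3 by the planned completers). In arms of that size, chance differences in starting pain can be appreciable. No treatment effect can exist at a reading taken before treatment, so averaging that reading into a group effect pulls the arm difference toward zero and leaves stable between-subject differences in pain in the error. An unnamed covariate could also be chosen after the data are seen.

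**Working it through.** **The plan's own power figures.** Section 6 gives power 0.966 with 24 subjects (POSAS) and 0.962 with 33 (DVPRS). Neither can be derived from the stated inputs, because the effect size f, the number of readings, the correlation and the effect tested are not given. One assumed set returns both: 3 groups, 4 readings, correlation 0.2, a within-subject time effect, f = d√(1/6), with d = 1 for POSAS and d = 2/2.4 for DVPRS. It gives 0.9662 and 0.9618. Other sets match each figure singly, so this proves nothing about what was run. These figures do not settle how baseline is used.

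**Set-up for the comparison.** Each reading has variance 1. There are p readings after baseline, with equal correlation ρ between any two readings, as a single random subject effect implies. The arm difference is constant at all p readings. The documents give no ρ, so 0.3, 0.5 and 0.7 are shown. With one reading per visit, p = 4. Variances below are per subject and on the scale of the undiluted arm difference.

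1. *Group main effect, baseline among the p + 1 readings.* The effect is multiplied by p/(p+1): 4/5 with 5 readings (20% dilution), 8/9 with 9 (11%). The rescaled variance is [(1 + pρ)/(p+1)] × [(p+1)/p]².
2. *Baseline as covariate, mean of the p later readings.* [1 + (p−1)ρ]/p − ρ².
3. *Mean change from baseline over p visits.* [1 + (p−1)ρ]/p + 1 − 2ρ.
4. *Change at one visit.* 2(1 − ρ), against 1 − ρ² with adjustment. The ratio is (1 + ρ)/2.

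Results for p = 4:

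| ρ | (1) pooled | (2) adjusted | (3) mean change | loss, (1) vs (2) | loss, (3) vs (2) | loss, one-visit change |
|---|---|---|---|---|---|---|
| 0.3 | 0.6875 | 0.385 | 0.875 | 44% | 56% | 35% |
| 0.5 | 0.9375 | 0.375 | 0.625 | 60% | 40% | 25% |
| 0.7 | 1.1875 | 0.285 | 0.375 | 76% | 24% | 15% |

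Example at ρ = 0.5: (1) is (3/5) × (5/4)² = 0.9375; (2) is 2.5/4 − 0.25 = 0.375; 1 − 0.375/0.9375 = 60%.

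The ratio of (2) to (1) simplifies to (1 − ρ)p/(p+1). The loss therefore exceeds half only when ρ is above 0.375 (5 readings) or 0.4375 (9 readings). With 9 readings and an equal effect at all 8 later ones, it is 38%, 56% and 73%.

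5. *Baseline kept as an outcome, arm means constrained equal there.* The variance equals that of (2), so the loss is 0%.

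**In terms of power.** Take SD 2.4 from Section 6, 16 per arm, two-sided 0.05, and assume an arm difference of 0.5 × 4.4 = 2.2 points (2.2/2.4 = 0.917 SD). By the normal approximation, power is Φ(0.917/√(2V/16) − 1.96). For ρ = 0.3, 0.5 and 0.7, method (1) gives 0.878, 0.764 and 0.662; method (2) gives 0.987, 0.989 and 0.998. Section 6 states the 50% goal for pain reduction, not for a difference between arms, so 2.2 is illustrative. At a difference of 1.5 points the figures are 0.568, 0.447 and 0.368 against 0.813, 0.823 and 0.912.

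**The case against.** The strongest reply is that an analysis of covariance has a covariate by definition, and the baseline score is the natural candidate. The sentence listing group and time sits under the sample-size heading, where it explains which effects are random and which fixed; it need not be the full model. This stands to the extent that one cannot say the plan excludes baseline adjustment. It does not settle the matter, because weight, analgesic use and treatment expectation are also recorded at Visit 1 and nothing says which of these, if any, is meant.

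Three stronger readings are tempting, and the documents do not support them.

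- *That the plan treats the Visit 1 score as an outcome reading.* A reader might infer this from the count of 9 DVPRS procedures in Section 3. That table counts completed forms and says nothing about the model.
- *That most of the precision is thrown away.* This needs the pooled main effect and a correlation above 0.375 (5 readings), or a mean-change comparison at a low correlation. The documents give no correlation. The primary outcome and the planned contrasts also fit a comparison of change, which has no dilution.
- *That keeping baseline among the outcomes is itself the fault.* The constrained model does so and loses nothing.

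It can also be objected that simply limiting the outcome to Visits 2 to 5 would discard the Visit 1 post-treatment reading. The hypotheses in Section 2 concern acute as well as longer-term reduction, and that reading is the first acute one. This is correct, and the fix allows for it.

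**Conclusion.** The concern holds as a failure to commit. Followed literally, Section 6 does not adjust for a baseline score that the trial already collects, and its statements of effects, power basis and test do not fit together. Across the readings examined without adjustment, the loss runs from 15% to 76% of the information over correlations of 0.3 to 0.7 with one reading per visit. It is zero only under a constrained-baseline model, which the plan does not describe. These sizes rest on compound symmetry, a constant effect after Visit 1 and assumed correlations. They show what is at stake and are not an estimate of this trial's actual loss. The change is worth making because the data are already planned and the arms are small.

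**What to change.** In Section 6, for DVPRS and POSAS alike, state that:

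- the rANCOVA covariate is the Visit 1 pre-treatment score of the same scale (in Group 3, the single Visit 1 score);
- fixed effects are group, visit, group-by-visit and that score, with subject random; or, equivalently, Visit 1 is kept in the outcome vector with arm means constrained equal there;
- arms are compared on one reading per visit that all three arms have: the pre-treatment reading at Visits 2 to 4 (the single reading in Group 3) and the Visit 5 reading;
- post-treatment readings, including the one at Visit 1, go into a separate baseline-adjusted acute comparison of Groups 1 and 2;
- within-arm change from Visit 1 is reported alongside, since the Section 2 hypotheses concern reduction within each treatment.

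Bring the design sentence under the sample-size heading into line with this, and say how the rANOVA power basis relates to it.

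The cost is wording, one degree of freedom for the covariate and a little more analysis work. No additional data are needed.
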